13. STATISTICAL CONSIDERATIONS

13.1 Study Design/Endpoints

The primary endpoint will be the proportion of patients alive at 12 months (OS12). OS12 was selected as the primary endpoint as this avoids the confound of measuring progression in immunotherapy trials where pseudoprogression can complicate the analysis. OS12 will be defined from the time of study entry to death from any cause. Patients will be enrolled as one cohort (i.e. 1 stage design).

Recent studies in newly diagnosed GBM testing novel agents have suggested that OS12 is ~60% (Gilbert 2014, Lee 2015, Gilbert 2013). This number serves as a framework for our sample size calculations. The primary outcome will be evaluated by the Kaplan-Meier estimate as well a simple proportion. If the true OS12 increased by 20%, there would definitely be interest in further investigation of bavituximab. This study will test the null hypothesis (H0) with power and significance level of 0.89 and 0.09 respectively, that OS12 is \leq 60% versus the alternative hypothesis (Ha) that OS12 is \geq 80%. The total evaluable sample size is 33 with a total of 36 potential patients to be enrolled if there are inevaluable patients. Inevaluable patients are defined as patients who drop out prior to receiving bavituximab. Data for subjects who are lost to follow up prior to documented death will be counted as deaths at the last assessment date when the subject is known to be alive. Given our patient population, we anticipate the number of patients lost to follow-up to be very small and we will able to establish vital status at 12 months (the primary endpoint) even if patients drop out prior to 12 months. Vital status can be determined by searching death records as well.

We will test the relationship between other prognostic factors (specifically MGMT methylation status, age) and survival by using a Cox proportional hazards model. Another prognostic factor, KPS, was not included because all the patients have to have a good functional status to enroll.

13.2 Sample Size, Accrual Rate and Study Duration

A total of 36 evaluable participants will be accrued within 2 years, anticipating 3 patients enrolled per month. An additional 12 months of follow-up will be required on the last participant accrued to observe the participant's OS12. Patients will be followed for an additional 3 years for progression and survival data for secondary endpoint analysis.

Accrual targets below reflect the demographics of our area as well as the slight preponderance of GBM in males.

Accrual Targets				
Ethnic Catagory	Sex/Gender			

NCI Protocol #: DF/HCC Protocol #: 17-037 Protocol Version Date: September 25, 2018

		Females		Males		Total
Hispanic or Latino	2		+	3	=	5
Not Hispanic or Latino	14		+	17	=	31
Ethnic Category: Total of all subjects		16	+	20	=	36
Racial Category						
American Indian or Alaskan Native	0		+	0	=	0
Asian	2		+	3	=	5
Black or African American	2		+	2	=	4
Native Hawaiian or other Pacific Islander	0		+	0	=	0
White	11		+	15	=	27
Racial Category: Total of all subjects		16	+	20	=	36

13.3 Analysis of Primary Endpoints

See above – Section 13.1

13.4 Analysis of Secondary Endpoints

The radiographic response proportion (RR), progression-free survival (PFS), overall survival (OS), and toxicity proportion will each be described with 95% confidence limits. Radiographic response is defined as a complete response or partial response, as determined by the RANO criteria with incorporation of iRANO criteria (Okada 2015). The radiographic response rate is the proportion of subjects who have a radiographic response. Data for subjects without disease progression or death at the time of analysis or who are lost to follow up prior to the documented disease progression free. PFS is defined as the time of study entry to time of disease progression. Overall survival is defined as the time of study entry to death from any cause. Data for subjects who are lost to follow up will be censored at the date when the subject is last known to be alive. Kaplan-Meier methods will be used to estimate PFS/OS.

As data permit, exploratory analyses of blood biomarkers and MRI parameters will be summarized by descriptive statistics, including mean, median and standard deviation. Differences in these biomarkers between responders and non-responders will be compared with parametric or nonparametric techniques as permitted by the data. For correlative analyses, Cox proportional hazards model will be used to explore the relationship between these biomarkers measured at baseline and PFS and OS. Change in biomarkers during treatment will also be explored and their ability to serve as pharmacodynamics markers of response will be assessed.

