11.1.6 Progression-Free Survival

Overall Survival: Overall Survival (OS) is defined as the time from start of treatment to death due to any cause, or censored at date last known alive.

Progression-Free Survival: Progression-Free Survival (PFS) is defined as the time from start of treatment to the earlier of progression or death due to any cause. Participants alive without disease progression are censored at date of last disease evaluation.

Time to Progression: Time to Progression (TTP) is defined as the time from start of treatment to progression, or censored at date of last disease evaluation for those without progression reported.

11.1.7 Response Review

Response will be determined by the treating physician but all MRIs scans will be collected for later, central review of response by [name] and her team members.

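### Sections 13.4 and 11.1.6 define PFS with different events and different time zeros; OS shares the time-zero conflict, and nothing says which section governs

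*Combined protocol and SAP*

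**What the plan says.** **PFS.** Section 13.4 (secondary endpoint analysis) states "PFS is defined as the time of study entry to time of disease progression". Section 11.1.6 states "Progression-Free Survival (PFS) is defined as the time from start of treatment to the earlier of progression or death due to any cause", and adds the censoring rule "Participants alive without disease progression are censored at date of last disease evaluation".

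**TTP.** Section 11.1.6 keeps this as a separate endpoint: "Time to Progression (TTP) is defined as the time from start of treatment to progression, or censored at date of last disease evaluation".

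**OS.** Section 11.1.6 has "Overall Survival (OS) is defined as the time from start of treatment to death due to any cause"; Section 13.4 has "Overall survival is defined as the time of study entry to death from any cause". For the primary endpoint, Section 13.1 says "OS12 will be defined from the time of study entry to death from any cause".

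**Censoring in 13.4.** The sentence before the PFS definition opens with "Data for subjects without disease progression or death at the time of analysis", but in the text available to us it breaks off without stating a rule.

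Study entry is not tied to a date anywhere. Section 4.1 requires registration before protocol therapy begins, so entry and start of treatment can be different days. No section says whether 11.1.6 or 13.4 prevails.

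**The concern.** Two analysts could each follow the protocol and obtain different PFS results from the same data. One would count a death without documented progression as a failure; the other would not. The second result is a time to progression carrying the PFS label. In a single-arm study PFS is likely to be compared with other trials, so the label has to match what was estimated. PFS is also an outcome in the exploratory Cox models for biomarkers in 13.4, and those would inherit the ambiguity.

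The time-zero conflict touches PFS and OS. Because study entry is undated, it also leaves the start of the 12-month clock for OS12 to be inferred.

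**Working it through.** **1. Definitions side by side**

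| Endpoint | Section 11.1.6 | Sections 13.1 and 13.4 |
|---|---|---|
| PFS event | earlier of progression or death | progression |
| PFS time zero | start of treatment | study entry |
| TTP event | progression | not defined |
| OS time zero | start of treatment | study entry |
| OS12 time zero | not defined | study entry |

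The PFS event in 13.4 is the TTP event in 11.1.6.

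**2. The plan's own design figure.** The plan states 33 evaluable patients, 60% versus 80% alive at 12 months, significance level 0.09 and power 0.89. It gives no cut-off. With an inferred rule of success at 24 or more alive, the exact binomial gives:

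- P(X ≥ 24 | n = 33, p = 0.60) = 0.0923
- P(X ≥ 24 | n = 33, p = 0.80) = 0.8932

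Both match as printed. Neither depends on how PFS is defined.

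**3. Size of the event difference.** Let s be the share of first events that are deaths without documented progression. The documents do not give s, so 0, 2, 5 and 10% are assumptions. With constant hazards and such deaths censored at death, the progression hazard is (1 − s) times the PFS hazard, so:

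- ratio of medians (13.4 literal to 11.1.6) = 1/(1 − s)
- literal 13.4 estimate where true PFS is 50% = 0.5^(1 − s)
- expected reclassified events, if all 33 patients have an event = 33s
- chance that no patient is affected = (1 − s)^33

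| s | Ratio of medians | Estimate where true PFS is 50% | Reclassified of 33 | Chance none affected |
|---|---|---|---|---|
| 0% | 1.000 | 50.0% | 0 | 100% |
| 2% | 1.020 | 50.7% | 0.7 | 51% |
| 5% | 1.053 | 51.8% | 1.7 | 18% |
| 10% | 1.111 | 53.6% | 3.3 | 3% |

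For scale, the 95% half-width for a proportion of 50% with 33 patients and no censoring is 1.96 × √(0.25/33) = 17.1 points.

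**4. Sensitivity to the assumptions**

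- *Censoring at the last 8-weekly evaluation*, closer to the TTP rule in 11.1.6. Simulation with assumed median PFS of 6, 8 and 12 months gives median increases of about 2, 5 and 10% for s = 2, 5 and 10%.
- *Deaths without progression that come late* (Weibull shape 2, tuned to the same s, censored at death). The increases are about 0.7, 2 and 4%.

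**5. Direction.** With censoring at death, the progression-only curve cannot fall below the PFS curve. With censoring at the last evaluation the tendency is the same, but it is not guaranteed at every time point.

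**6. Time zero.** The documents give no length for the interval from study entry to start of treatment, so no effect is calculated.

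**The case against.** The strongest reply is that 13.4 is loose shorthand. Its preceding sentence describes patients without an event as free of both progression and death, which makes sense only if death counts. Section 11.1.6 shows that the authors know the difference between PFS and TTP. This is a fair account of probable intent, and a reader should not infer that the sponsor deliberately chose a progression-only estimand. But the definition sentence in 13.4 is complete, omits death, and sits in the section an analyst would follow. Intent has to be inferred, and a definition should not require that.

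The effect is also likely to be small. Unexplained neurologic deterioration counts as progression (11.1.4.1) and follow-up is typically every 8 weeks (Section 10), so few deaths should arrive without documented progression. PFS is descriptive, with no test or decision attached. All of this stands, and it limits the weight of the point.

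Four stronger readings are tempting but not supported:

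- *The plan has no PFS censoring rule.* Section 11.1.6 has one, and the broken sentence in 13.4 may be damage from text extraction. It is not counted against the plan.
- *The time-zero conflict is worth several days.* With five weekday fractions and none missed, the first bavituximab infusion falls 3 to 7 days after the first radiation day. That measures the distance between two possible treatment starts, not between study entry and treatment.
- *Registration is the only dated clock.* Section 5.6 runs follow-up from registration, but 13.5.1 uses other dated anchors: completion of radiation, first treatment and last bavituximab dose.
- *The primary endpoint is contradicted.* Section 13.1 fixes study entry for OS12, 13.4 agrees for OS, and only the general OS definition in 11.1.6 differs. What is missing for OS12 is a date for study entry.

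**Conclusion.** The contradiction is real and should be fixed. The two sections give PFS different events and different origins, OS has different origins, and neither section is given precedence. Taken literally, 13.4 reports TTP as PFS and tends to overstate it: about 2, 5 or 11% on the median if 2, 5 or 10% of first events are deaths without progression. Those shares are assumed, and the percentages rest on constant hazards and censoring at death; late deaths would make the increases smaller. Where true PFS is 50%, the shift is at most 3.6 points (53.6 − 50.0) over this range, well inside the 17-point half-width.

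The time-zero conflict is confirmed from the text, but its size is unknown. The OS12 sample size, significance level and power are unaffected. This is a fault in the definition of a descriptive secondary endpoint, not a design failure.

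**What to change.** - **Event and censoring.** In 13.4, use the protocol's own 11.1.6 rule: the event is the earlier of progression or death from any cause, and patients alive without progression are censored at their last disease evaluation. Report progression-only time as TTP.
- **Time zero.** Choose one dated origin and apply it to OS12, OS, PFS and TTP alike in 13.1, 13.4 and 11.1.6. Defining study entry as the date of registration is one option. Another dated origin would also serve, provided that it is fixed before analysis and that PFS and TTP keep a common start.
- **Start of treatment.** Wherever this remains an origin, such as duration of stable disease in 11.1.5, say which date it means. Section 5.2.1 places the first bavituximab dose on day 1 of cycle 1, while the Section 10 calendar places it between the 4th and 6th radiation treatments. These passages must be reconciled.

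The cost is wording only, with no change to sample size, significance level or power. Reported PFS may be slightly shorter than under the literal 13.4 text.

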13.5 Reporting and Exclusions

13.5.1 Evaluation of Toxicity

All participants will be monitored for 90 days from completion of radiation in order to assess for any AEs related to radiation and bavituximab regardless of duration of bavituximab.

Otherwise, all participants will be evaluable for toxicity from the time of their first treatment until 30 days after the last dose of bavituximab.

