10. STUDY CALENDAR

Baseline evaluations are to be conducted within 2 weeks prior to start of protocol therapy. Scans must be done \leq 2 weeks prior to the start of therapy. In the event that the participant's condition is deteriorating, laboratory evaluations should be repeated within 48 hours prior to initiation of the next cycle of therapy.

Assessments must be performed prior to administration of any study agent. Study assessments and agents should be administered within \pm 3 days of the protocol-specified date, unless otherwise noted.

	Pre-	Wk	Wk	Wk	Wk	Wk	Wk	Off Treatment ^e
	Study	1^{g}	2	3	4	5	6	On meannent
Bavituximab		Х	Х	Х	Х	х	Х	
Temozolomide		Х	Х	Х	Х	х	Х	
Radiation ^J		Х	Х	Х	Х	х	х	
Informed consent	Х							
Demographics	Х							
Medical history	Х							
Concurrent meds	Х	Х		Х			Х	
Physical exam ¹	Х	Х		Х			Х	Х
Vital signs ¹	Х	Х	Х	Х	Х	х	х	Х
Height	Х							
Weight ¹	Х	Х		Х			Х	
Performance status ¹	Х	Х		Х			Х	Х
Drug diary for temozolomide ^h		Х	X	Х	Х	X	Х	

Cycle 1: Radiation + temozolomide + bavituximab

CBC w/diff, plts	Х	X	Х	Х	Х	Х	Х	х
Serum chemistry ^a	Х			х				х
PT/INR/aPTT	Х							
ECG (as indicated)i	Х							
Adverse event evaluation		X		Х			х	Х
Tumor measurements via MRI ^b	Х							Х
B-HCG °	Х							
Tissue ^{d, k}	Х							
Correlative Blood Draws f	Х						Х	

b- MRI to be done at the Martinos Center for Biomedical Imaging

c – Serum Pregnancy Test (for women of childbearing potential)

d – Assessment to determine if there is sufficient tissue for correlative studies. Tissue may be sent as a batch later to minimize shipping requirements. Tissue is not required for registration.

e- This column included in case patient goes off study during cycle 1. This visit can occur within 2 weeks of the participant coming off study.

f – See section 9.2. Blood will be drawn prior to start of chemoradiation and during week 6 of chemoradiation.

g- First bavituximab infusion should happen after the 4th radiation treatment and before the 6^{th} treatment.

h- See Appendix B for the required drug diary.

i - if ECG is clinically indicated, the QTc-B rather than QTc-F should be used to look for abnormalities

J – Radiation dose not have to be done at a DFHCC site but should be considered to allow for ease of dosing bavituximab during radiation

K – MGMT status will be collected but is not required for registration

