1 -if it is determined that a patient will not be coming in for bavituximab on a specific day (ex. due to treatment hold or scheduling conflicts), then the patient does not need to return to clinic solely for the physical exam, weight, KPS, and vital sign assessments as theses were intended to be done prior to the infusion as a safety check.

Cycle 2: Post-Radiation – bavituximab monotherapy

Labs should be drawn up to 3 days prior to bavituximab dosing.

	Wk 1	Wk 2	Wk 3	Wk 4	Off Treatment ^e
Bavituximab	Х	Х	Х	Х	
Concurrent meds		Х		Х	
Physical exam ^g		Х		Х	Х
Vital signs ^g	Х	X	Х	Х	Х

Weight ^g		Х	Х	
Performance status ^g		Х	Х	Х
CBC w/diff, plts	Х			Х
Serum chemistry ^a	Х			Х
Adverse event evaluation		Х	Х	Х
Tumor measurements via MRI ^b			х	Х
Correlative Blood draws ^f	Х			

b- MRI to be done at the Martinos Center for Biomedical Imaging. This should be done at any time during the 4-5 weeks after completion of radiation but within 1 week of starting post-RT temozolomide.

e- This column included in case patient goes off study during cycle 2. This visit can occur within 2 weeks of the participant coming off study.

f-See section 9.2

g - if it is determined that a patient will not be coming in for bavituximab on a specific day (ex. due to treatment hold or scheduling conflicts), then the patient does not need to return to clinic solely for the physical exam, weight, KPS, and vital sign assessments as theses were intended to be done prior to the infusion as a safety check.

	Wk 1	Wk 2	Wk 3	Wk 4	EOT/Off Study ^e	Follow-up ⁱ
Bavituximab	х	Х	Х	Х		
Temozolomide ^g	Х					
Drug diary for temozolomide ^h	х					
Concurrent meds		Х				
Physical exam ^k		Х		Х	Х	
Vital signs ^k	Х	Х	Х	Х	Х	
Height						
Weight ^k		Х			Х	
Performance status ^k		Х		Х	Х	
CBC w/diff, plts ^j			Х	Х	Х	
Serum chemistry ^a	х				Х	
EKG/coag panel (as indicated)						
Adverse event evaluation		Х		Х		
Tumor measurements via MRI ^b						Х

Cycle 3: Monthly temozolomide + bavituximab therapy

Correlative Blood draws ^f	Х			

b- EOT MRI to be done at the Martinos Center for Biomedical Imaging if possible

e- EOT = end of treatment. For patients removed from the study for one of the criteria in Section 5.5 during cycle 3 or 4 or has completed treatment after cycle 4, this information should be collected within 28 days of the last bavituximab dose. Follow-up of AE resolution to </= grade 1 or baseline may be beyond 28 days.

f - See section 9.2

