g- Temozolomide is administered for 5 consecutive days during week 1 of the cycle

h - See Appendix B for the required drug diary.

i – Participants will be followed for progression via MRI or clinic assessment per standard of care which is typically every 8 weeks as well as overall survival for up to 3 years. MRIs will be collected for central review. If MRI is not performed at Martinos, it should be sent to the study PI on a DVD or contact [name] for electronic transfer instructions.

j-CBC with diff should align with standard of care assessments on day 21± 3 days and day 28 ± 3 days of each cycle.

K - if it is determined that a patient will not be coming in for bavituximab on a specific day (ex. due to treatment hold or scheduling conflicts), then the patient does not need to return to clinic solely for the physical exam, weight, KPS, and vital sign assessments as theses were intended to be done prior to the infusion as a safety check.

ej 110 11 11 10 11 11 11 11 11 11 11 11 11						
	Wk 1	Wk 2	Wk 3	Wk 4	EOT/Off Study ^e	Follow-up ⁱ
Bavituximab	Х	Х	Х	х		
Temozolomide ^g	Х					
Drug diary for temozolomide ^h	х					
Concurrent meds		Х				
Physical exam ^k		Х		х	Х	
Vital signs ^k	х	Х	Х	х	Х	
Height						
Weight ^k		Х			Х	
Performance status k		X		Х	Х	
CBC w/diff, plts ^j			Х	Х	Х	
Serum chemistry ^a	Х				Х	
EKG/coag panel (as indicated)						
Adverse event evaluation		X		х		
Tumor measurements via MRI ^b				х	Х	Х
Correlative Blood draws f	Х					

Cycle 4: Monthly temozolomide + bavituximab therapy

a- Serum chemistry panel should include albumin, alkaline phosphatase, total bilirubin, BUN,

chloride, creatinine, glucose, potassium, total protein, AST/SGOT, ALT/SGPT, sodium. b- MRI to be done at the Martinos Center for Biomedical Imaging. The MRI scan should be performed at any time during the 4th week of the cycle.

e- EOT = end of treatment. For patients removed from the study for one of the criteria in Section 5.5 during cycle 3 or 4 or has completed treatment after cycle 4, this information should be collected within 28 days of the last bavituximab dose. Follow-up of AE resolution to </= grade 1 or baseline may be beyond 28 days.

f - See section 9.2

g- Temozolomide is administered for 5 consecutive days during week 1 of the cycle

h - See Appendix B for the required drug diary.

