i – Participants will be followed for progression via MRI or clinic assessment per standard of care which is typically every 8 weeks as well as overall survival for up to 3 years. MRIs will be collected for central review. If MRI is not performed at Martinos, it should be sent to the study PI on a DVD or contact [name] for electronic transfer instructions.

j - CBC with diff should align with standard of care assessments on day 21 ± 3 days and day 28 ± 3 days of each cycle.

k- if it is determined that a patient will not be coming in for bavituximab on a specific day (ex. due to treatment hold or scheduling conflicts), then the patient does not need to return to clinic solely for the physical exam, weight, KPS, and vital sign assessments as theses were intended to be done prior to the infusion as a safety check.

Please note, patients may continue bavituximab beyond 18 weeks at the discretion of the treating physician if the patient is deriving clinical benefit. If the patient also continues temozolomide, the dosing of concomitant temozolomide will be per institutional standard of care so not included in the Table for Cycle 5 and beyond but can be given in conjunction with bavituximab if previously tolerated.

V					1.4	
	Wk 1	Wk 2	Wk 3	Wk 4	EOT/Off Study ^e	Follow-up ⁱ
Bavituximab ^k	Х	Х	Х	Х		
Concurrent meds		Х				
Physical exam ¹		Х		Х	Х	
Vital signs ¹	х	Х	Х	Х	Х	
Height						
Weight				Х	х	
Performance status				Х	Х	
CBC w/diff, plts				Х	Х	
Serum chemistry ^a	Х				Х	
EKG/coag panel (as indicated)						
Adverse event evaluation		Х		Х		
Tumor measurements via MRI ^b				X ^b	Х	Х

Cycle 5 and beyond: Bavituximab therapy

Correlative Blood draws ^f	Х			

b- If possible, MRI to be done at the Martinos Center for Biomedical Imaging. The MRI scan should be performed at any time during the 4th week of every other cycle, starting with Cycle 6, to align with standard of care timepoints. If MRI during the study duration is not performed at Martinos, it should be sent to the study PI on a DVD or contact [name] for electronic transfer instructions.

e- EOT = end of treatment. For patients removed from the study for one of the criteria in Section 5.5 during cycle 5 or beyond, this information should be collected within 28 days of the last bavituximab dose. Follow-up of AE resolution to </= grade 1 or baseline may be beyond 28 days.

f – See section 9.2

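### No adverse event check in the study calendar closes the 30-day or the 90-day toxicity window of Section 13.5.1, so new, mainly non-serious events late in those windows have no scheduled ascertainment

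*Combined protocol and SAP*

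**What the plan says.** Section 13.5.1 sets two windows. The general one: "all participants will be evaluable for toxicity from the time of their first treatment until 30 days after the last dose of bavituximab". The other is tied to radiation and applies however long bavituximab was given: "All participants will be monitored for 90 days from completion of radiation in order to assess for any AEs related to radiation and bavituximab".

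Section 10 sets the visits.

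- **Cycles 1 and 2.** AE evaluation is marked in the Off Treatment column. Footnote e on timing: "This visit can occur within 2 weeks of the participant coming off study".
- **Cycles 3, 4 and 5+.** AE evaluation is marked at weeks 2 and 4 only. The EOT/Off Study and Follow-up cells are blank in all three tables, although physical exam, vital signs, weight, performance status, CBC and chemistry are marked at EOT. Footnote e on EOT timing: "this information should be collected within 28 days of the last bavituximab dose". No earliest day is given. The same footnote adds: "Follow-up of AE resolution to </= grade 1 or baseline may be beyond 28 days".
- **Follow-up column.** Footnote i describes it in terms of progression and survival.

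Toxicity is a secondary objective (Section 1.3). Section 13.4 reports it as a proportion with 95% confidence limits.

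**The concern.** A toxicity proportion is only as complete as the questioning behind it. Section 13.5.1 treats every participant as evaluable to 30 days after the last dose, and monitored to 90 days after radiation. If nobody is scheduled to ask about AEs near those dates, the analysis claims observation time that the visit schedule does not deliver. A missed event can move the proportion in one direction only. With 33 evaluable or 36 enrolled patients (Section 13.1), each patient whose only qualifying event is missed lowers the proportion by 1/36 to 1/33, or about 3 percentage points. Delayed events are the most exposed, and so are patients who stop early and leave the weekly visit schedule.

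**Working it through.** The plan gives no figure to reproduce here, so the check is a day count against the calendar.

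**Inputs.** Cycle 1 is 6 weeks and later cycles are 4 weeks (Section 5.1). This gives 6 + 3 × 4 = 18 weeks, matching the active period in Section 5.3.2. The windows are 30 and 90 days (Section 13.5.1). EOT is due by day 28 after the last dose, and the cycle 1-2 off-treatment visit within 14 days (Section 10).

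**Assumptions.** Day 0 is the end of radiation and the start of cycle 2. Doses fall at the start of each week. A week's AE check may fall on any of its 7 days. The 2 weeks for the off-treatment visit are counted from the last dose.

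**90-day window.** Days without a scheduled check = 90 − day of the last scheduled AE check.

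| Last dose | Day after radiation | Last scheduled AE check | Days left of 90 |
|---|---|---|---|
| End of cycle 1 | 0 | off-treatment visit, days 0-14 | 76-90 |
| Cycle 2 week 4 | 21 | off-treatment visit, days 21-35 | 55-69 |
| Cycle 3 week 4 | 49 | week 4, from day 49 | about 41 |
| Cycle 4 week 4 (18-week completer) | 77 | week 4, days 77-83 | 7-13 |
| Cycle 5 week 4 | 105 | week 4, past day 90 | 0 |

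- For the cycle 3 stopper, 41 counts from the last dose. A week-4 check on the last day of that week (day 55) would leave 90 − 55 = 35. The latest EOT is day 49 + 28 = 77, so even an AE item there would leave 90 − 77 = 13 days.
- For the 18-week completer, the latest EOT is day 77 + 28 = 105, past day 90, but it carries no AE item.
- Section 5.3.2 allows ±7 days on the start of each monthly temozolomide cycle. If cycles 3 and 4 both start 7 days early, cycle 4 week 4 is days 63-69 and 21-27 days are left. If both start 7 days late, week 4 is days 91-97 and none is left. The completer's range is therefore 0 to 27 days.
- Cycle 5 starts at day 84, so its week-2 check falls at day 91 or later. Patients who continue through cycle 5 are checked past day 90.

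**30-day window.**

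- Stop at week 4 of cycle 3, 4 or 5+: the last scheduled check is 0-6 days after the last dose, so 30 − 6 = 24 to 30 days have none.
- Stop in cycle 1 or 2: the check is within 14 days, so at least 30 − 14 = 16 days have none.
- If the EOT cell were filled in, the latest permitted visit would still end 30 − 28 = 2 days short. An earlier visit would leave more.

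**Does the 3-monthly follow-up in Section 5.6 fill the gap?** Assume registration 0-14 days before radiation and 42 days of radiation. The first two contacts then fall about 91 − 42 − (0 to 14) = 35 to 49 and 183 − 42 − (0 to 14) = 127 to 141 days after radiation. Neither is near day 90, and the AE focus stated there is late radiation effects.

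**The case against.** The strongest reply is that the calendar is not the only source of AE data. Section 13.5.1 is itself an instruction to monitor. Section 7.3.1 requires serious events to be reported to 30 days after the last dose. Section 7.6 sends all AEs to the toxicity case report forms, with no restriction by visit. Section 5.6 follows patients removed for AEs to resolution or stabilization and records late radiation effects. A clinical EOT visit with exam and laboratory tests does take place, and footnote e presupposes that AE status is known by then. Nor is a blank EOT cell conclusive: the cycle 3 table leaves the EOT MRI cell blank while its footnote b describes an EOT MRI.

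Most of this stands, and it limits the point. A reader might infer that toxicity in these windows goes uncollected altogether; the provisions above rule that out. What they do not supply is an occasion for finding new non-serious events. Section 7.3.1 is confined to serious events, Section 7.6 attaches no visit, and footnote e and the resolution rule follow events already known. The blank AE cell may be one omission copied across three similar tables. That would be a reason to correct it, and filling it would still leave both windows open for some patients.

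The consequences are also bounded. The primary endpoint, survival at 12 months, is unaffected. The toxicity halting rule in Section 12.2 concerns the first 20 patients followed over 4 weeks and does not depend on the later EOT cells.

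**Conclusion.** The point holds as a mismatch between the analysis windows and scheduled ascertainment. No calendar visit closes either window by design, and the effect on a descriptive secondary outcome can only be downward. The table gives the nominal size; it rests on 4-week cycles without delays and on the timing assumptions stated there.

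Two stronger readings are not supported. First, a reader might place the 90-day problem mainly in cycle 3 and later, where the EOT cells are blank. The largest 90-day gaps belong to patients who stop in cycles 1 and 2, whose off-treatment visit does include an AE check but comes early. From cycle 3 on, only those who stop during cycle 3 have a sizeable gap on nominal timing. Second, a reader might take the unscheduled share of the window as the size of the undercount. It is a share of calendar time. The documents give no rate of late-onset events, and an AE check can record events since the previous visit, so the size of any bias cannot be calculated.

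**What to change.** Reconcile Section 10 with Section 13.5.1 in two steps.

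1. Mark AE evaluation in the EOT/Off Study column of the cycle 3, 4 and 5+ calendars.
2. Add one AE contact for every participant, including those who stop in cycle 1 or 2, at the later of 30 days after the last bavituximab dose and 90 days after completion of radiation. A phone call is enough; Section 5.6 already uses calls to establish status.

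The cost is a calendar amendment and one extra phone contact per patient. The reported toxicity rate may come out slightly higher, because more of the events in the stated windows would be found.
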